5.2 Withdrawal of subjects from study

5.2.1 Withdrawal

Subjects **must be withdrawn from the trial** (treatment and procedures) for the following reasons:

- Subject withdraws consent from study treatment and study procedures. A subject must be removed from the trial at his/her own request or at the request of his/her legally acceptable representative. At any time during the trial and without giving reasons, a subject may decline to participate further. The subject will not suffer any disadvantage as a result.
- Pregnancy. Pregnancy will be reported with the same time lines as SAE. (Note: subjects who have been withdrawn from treatment with study drug because of

pregnancy should not undergo CT scans [with contrast]/MRI or bone scans while pregnant.)

- If, in the investigator's opinion, continuation of the trial would be harmful to the subject's well-being.
- Subject is lost to follow-up.

Subjects **may be** withdrawn from the study for the following reasons:

- The subject is non-compliant with study drug, trial procedures, or both; including the use of anti-cancer therapy not prescribed by the study protocol.
- Severe allergic reaction to regorafenib (such as exfoliative erythroderma or Grade 3 or 4 hypersensitivity reaction).
- The development of a second cancer.
- Development of an intercurrent illness or situation which would, in the judgment of the investigator, significantly affect assessments of clinical status and trial endpoints.
- Deterioration of ECOG performance status to 4.
- Use of illicit drugs or other substances that may, in the opinion of the investigator, have a reasonable chance of contributing to toxicity or otherwise skewing trial result.

Any subject removed from the trial will remain under medical supervision and followed until discharge or transfer is medically acceptable.

In all cases, the reason for withdrawal (progression vs. toxicity vs. patient's choice) must be recorded in the CRF and in the subject's medical records.

5.2.2 Screen Failures/Dropouts

A subject who discontinues study participation prematurely for any reason is defined as a "dropout" if the subject has already been administered at least one dose of study drug.

A subject who, for any reason (e.g. failure to satisfy the selection criteria), terminates the study before the time point used for the definition of "dropout" (see above) is regarded a "screening failure".

5.2.3 Replacement

During phase I, for subject who dropout due to reasons other than toxicity, we will replace that subject with another subject. These subjects will be followed for PFS.

6. Treatment[s]

6.1 Treatments to be administered

Drug	Dose/Potency	Dose Frequency	Route of Administration
Pembrolizumab	200mg	Q3weeks	IV
Regorafenib	Per dose schedule (phase I) RD (Phase II)	Daily days 1-14 of 21 day cycles	PO

Regorafenib starting dose, dose level 1	80mg	Days 1-14
Regorafenib dose level 2	120mg	Days 1-14

6.2 Treatment assignment

This is an open label phase I/II trial. Patients will receive regorafenib at escalating doses or RD for 14 days and pembrolizumab q3weeks.

All patients (phase I and II) will be seen on a weekly basis for the first 8 weeks for toxicity checks using CTCAE and will have response assessment with CT scan every 8 weeks.

Rules for dose escalation, dose expansion, and termination of escalation are given below.

Dose Limiting Toxicity (DLT)

As a general rule, DLT includes the observation of any of the side effects listed below during the DLT evaluation period and will ultimately be determined upon deliberation between subsites and the principal investigator of the trial. The principal investigator and the study team will have weekly safety meetings and conference calls during phase I period. Monthly meetings will be held monthly for the first 20 patients on phase II and if no unexpected signal of toxicity is observed the frequency of the meetings will be annual to correspond with the reporting period to Data and Safety Monitoring Committee at USC (DSMC). Furthermore, the opinion of the DSMC at USC can be sought as required on an ad hoc basis.

- Hematotoxicity:

- Persistent grade 4 neutropenia lasting ≥ 7 days;

- neutrophil count of $< 1000/\text{mm}^3$ with a single temperature of $> 38.3^\circ\text{C}$ or a sustained temperature of $\geq 38.0^\circ\text{C}$ for more than one hour.

- Grade 4 thrombopenia or thrombopenia associated with a hemorrhage requiring platelet transfusion.

- Grade 3 thrombocytopenia with bleeding.

- Grade 4 anemia.

- Non-hematotoxicity, please see separate liver and non-liver related information below.

- Liver related toxicities

- ALT/AST increases 5-8 X ULN with concomitant bilirubin increase $< 2 \times$

- ULN not resolving to $< 5 \times$ ULN within 7 days
 - ALT/AST increases $5-8 \times$ ULN with concomitant bilirubin increase $> 2 \times$ ULN
 - ALT/AST increases $> 8 \times$ ULN regardless of concomitant bilirubin increase
 - Bilirubin increase $> 3 \times$ ULN not resolving to baseline within 7 days
- Grade ≥ 3 non-liver related with the following specifications:
 - \geq Grade 3 diarrhea, nausea, vomiting, and loss of appetite for ≥ 5 consecutive days (despite supportive therapy);
 - \geq Grade 3 fatigue for ≥ 7 consecutive days;
 - \geq Grade 3 electrolyte imbalance for ≥ 7 consecutive days (despite supportive therapy);
 - Grade 3 dermatologic toxicity (HFSR and non-life threatening events) for ≥ 7 consecutive days;
 - Grade 4 dermatologic toxicity of any duration;
 - \geq Grade 3 immune-related adverse events lasting for ≥ 8 consecutive days despite steroid therapy.

• Combination therapy:

When 70% of the planned regorafenib dose cannot be administered because of toxicity other than DLT during the DLT evaluation period it will be considered DLT. This criteria is in place to ensure the combination can be delivered safely.

Maximum Tolerated Dose (MTD)

During the Phase I portion, the maximum tolerated dose (MTD) is defined as the highest dose tested in which none or only one patient experienced DLT, when at least 6 patients were treated at that dose and are evaluable for toxicity. The MTD is one dose level below the lowest dose tested in which 2 or more patients experienced DLT, unless dose level 3 is established as the MTD. At least 6 patients will be treated at the MTD.

Numbers of Patients and Rules for Dose Escalation

Rules for dose escalation and expansion in cohorts of patients are based on DLT occurring in each patient's first cycle of treatment (21 days without delay or interruption). The standard 3+3 rules will be used. Three patients will be treated at each new dose level. If 0/3 patients experience DLT, 3 patients will be treated at the next dose level. If DLT is experienced in exactly 1/3 patients, 3 more patients (for a total of 6) will be treated at that dose level. If no additional DLT is observed at the expanded dose level (i.e. 1/6 with DLT), the dose will be escalated. Escalation will terminate as soon as two or more patients experience any DLT at a given dose level. The Phase I trial will be closed when 6 patients have been treated at the next lower

dose level, and at most 1/6 patients experience DLT. If more than 1/6 patients experience DLT, the next lower dose will be expanded.

All patients who have not experienced any DLT must be observed for a minimum of 3 weeks after the start of the first cycle, before the dose level is escalated.

There will be no dose escalation within a patient.

Toxicities of interest for Pembrolizumab

- Pneumonitis
- Hepatitis
- Colitis
- Hypothyroidism
- Hypophysitis

Miscellaneous

For toxicities of interest for pembrolizumab and unexpected drug-related toxicity (even at lower grade) is seen more frequently than expected, this toxicity will be declared as unacceptable and a dose modification amendment will be made to the study necessitating dose reduction for that toxicity after thorough consultation between the investigator and the sponsor.

For certain toxicities such as laboratory assessments without a clear clinical correlation (e.g. lipase increase without signs of a clinical pancreatitis), a discussion between the investigator and the sponsor may take place if that adverse event should be considered unacceptable and a dose modification amendment will be made to the study necessitating dose reduction for that toxicity.

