7.3.1.1.3 Immune-mediated adverse reactions

Immune-mediated adverse reactions occurred in patients receiving pembrolizumab. In clinical trials, most immune-mediated adverse reactions were reversible and managed with interruptions of pembrolizumab, administration of corticosteroids and/or supportive care.

For suspected immune-mediated adverse reactions, ensure adequate evaluation to confirm etiology or exclude other causes. Based on the severity of the adverse reaction, withhold pembrolizumab and administer corticosteroids (see below). Upon improvement to Grade 1 or less, initiate corticosteroid taper and continue to taper over at least 1 month. Restart pembrolizumab if the adverse reaction remains at Grade 1 or less. If another episode of a severe adverse reaction occurs, permanently discontinue pembrolizumab.

Immune-mediated pneumonitis

Pneumonitis has been reported in patients receiving pembrolizumab. Monitor patients for signs and symptoms of pneumonitis. If pneumonitis is suspected, evaluate with radiographic imaging. Exclude other causes of pneumonitis, and manage treatment in accordance with the guidelines above. Administer corticosteroids, withhold pembrolizumab for moderate (Grade 2) pneumonitis, and permanently discontinue pembrolizumab for severe (Grade 3) or life-threatening (Grade 4) pneumonitis (see Immune-mediated adverse reactions above). If Grade 2 pneumonitis is repeated pembrolizumab will be discontinued permanently.

Immune-mediated colitis

Colitis has been reported in patients receiving PEMBROLIZUMAB. Monitor patients for signs and symptoms of colitis. Exclude other causes of colitis, and manage treatment in accordance with the guidelines above. Administer corticosteroids, withhold pembrolizumab for moderate (Grade 2) or severe (Grade 3) colitis, and permanently discontinue pembrolizumab for life-threatening (Grade 4) colitis (see Immune-mediated adverse reactions above).

Immune-mediated hepatitis

Hepatitis has been reported in patients receiving pembrolizumab. Monitor patients for changes in liver function (at the start of treatment, periodically during treatment and as indicated based on clinical evaluation) and symptoms of hepatitis. Exclude other causes of hepatitis, and manage treatment in accordance with the guidelines above. Administer corticosteroids and, based on severity of liver enzyme elevations, withhold or discontinue pembrolizumab (see Immune-mediated adverse reactions above).

Immune-mediated nephritis

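### Four DLT duration tests also bind Grade 4, so a short life-threatening event late in cycle 1 can meet no listed DLT criterion

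*Combined protocol and SAP*

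**What the plan says.** Section 6.2 opens its DLT list with "As a general rule, DLT includes the observation of any of the side effects listed below" and leaves the final call to deliberation between the subsites and the principal investigator. Non-hepatic toxicity at Grade 3 or above is introduced as "non-liver related with the following specifications". Four of those specifications set a minimum duration for Grade 3 and everything above it:

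- "Grade 3 diarrhea, nausea, vomiting, and loss of appetite for" at least 5 consecutive days despite supportive care;
- fatigue for at least 7 consecutive days;
- electrolyte imbalance for at least 7 consecutive days despite supportive care;
- "Grade 3 immune-related adverse events lasting for" at least 8 consecutive days despite steroids.

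The skin lines are split by grade. Grade 3 needs 7 days, but "Grade 4 dermatologic toxicity of any duration" is dose-limiting.

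A further criterion concerns delivery: "When 70% of the planned regorafenib dose cannot be administered because of toxicity other than DLT" in the evaluation period, the patient has a DLT. It has no counterpart for pembrolizumab. The evaluation period is the "first cycle of treatment (21 days without delay or interruption"), and Section 6.1 plans regorafenib on days 1 to 14 of it.

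**The concern.** Section 7.3.1.1.2 defines Grade 4 as life-threatening and needing urgent intervention. Under the four lines above, such an event that improves quickly is not a listed DLT. The skin lines show that the authors knew how to exempt Grade 4 from a duration test, and no reason is given for treating Grade 4 diarrhea or pneumonitis less strictly than Grade 4 rash.

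The toxicity-management rules apply no such test. Section 7.3.1.1.3 says to "permanently discontinue pembrolizumab for severe (Grade 3) or life-threatening (Grade 4) pneumonitis". Table 6.7 and Section 15.2 require the same for Grade 4 diarrhea, and the catch-all row of Section 15.2 for other Grade 4 immune-related events. One of the two study drugs can therefore be lost for good through an event that meets no DLT criterion.

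First-cycle DLT is the phase I endpoint (Section 10) and drives the rule of at most 1 DLT in 6 patients. For these events the count rests on case-by-case judgement instead of a written rule.

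**Working it through.** The plan gives no figure to reproduce. The check is whether any other listed criterion catches a short Grade 4 event of these types.

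**Inputs.** Planned regorafenib doses in cycle 1: 14 (Section 6.1). Delivery threshold: 70% (Section 6.2). Window: 21 days (Section 6.2).

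**Threshold in doses.** 0.70 × 14 = 9.8. If the rule means that at least 70% must be given, 10 doses are needed.

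**Doses given if dosing stops on onset day d and does not restart:** d − 1, up to 14.

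| Onset day | Doses given | Share of 14 | Below 70%? |
|---|---|---|---|
| 9 | 8 | 57% | yes, DLT |
| 10 | 9 | 64% | yes, DLT |
| 11 | 10 | 71% | no |
| 12 | 11 | 79% | no |
| 15 or later | 14 | 100% | no |

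The rule therefore cannot catch onset on days 11 to 21. Three variations open the gap earlier:

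- If the onset-day dose was taken, day 10 also yields 10 doses and escapes.
- If regorafenib restarts after a short hold, day 10 can escape. At 80 mg, a 3-day hold and then 80 mg every other day (on average 40 mg daily) gives (9 × 80 + 2 × 40) / (14 × 80) = 800/1120 = 71%.
- Read literally, the sentence requires that 70% could not be given. Stopping on day 5 loses 10/14 = 71% and counts; stopping on day 6 loses 9/14 = 64% and does not. The gap then opens at day 6.

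**Two hypothetical patients who meet no listed criterion:**

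- Diarrhea at Grade 3 or above on days 12 to 15 only, peaking at Grade 4. Duration 4 days, below 5 (and below 8 if judged immune-related). Doses given 11/14 = 79%. Table 6.7 requires permanent discontinuation of pembrolizumab.
- Immune-related pneumonitis at Grade 4 from day 15, down to Grade 2 by day 21. Days at Grade 3 or above: 15 to 20, that is 6, below 8. Doses given 14/14. Sections 7.3.1.1.3 and 15.2 require permanent discontinuation.

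**What is still caught.** The duration clock runs on all days at Grade 3 or above, so an event escapes only if it falls to Grade 2 or lower before the limit. ALT/AST above 8 times the upper limit counts at once, as do Grade 4 skin toxicity, anemia and thrombopenia. Events not named in the specifications, such as perforation, may count under the general Grade 3 heading.

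**The case against.** The strongest reply is that the list is only a general rule and that deliberation decides. Weekly safety meetings and a DLT committee (Section 1.1) make it unlikely that such an event would go unseen. Section 6.2 also allows a dose-modification amendment when a pembrolizumab toxicity of interest is more frequent than expected. All of this stands, and it rules out a stronger inference that a reader might draw, namely that these events cannot be counted. It does not make the written criterion right.

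A second reply is that duration at Grade 4 was deliberate: Grade 4 neutropenia must last 7 days, and the references to supportive care and steroids suggest an intention to count only toxicity that resists management. That is a possible preference. Neutropenia, however, is a laboratory count, so its test does not show that brief clinical emergencies were meant to be exempt.

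Two other stronger readings are not supported:

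- *That late-onset events can never satisfy a duration test.* This assumes the duration must be completed by day 21. The text does not say so, and it sets 3 weeks as a minimum observation time before escalation.
- *That treatment-related death is not a DLT.* No line names it, but Section 5.2.3 replaces phase I dropouts only for reasons other than toxicity, so counting a toxic death is the natural inference.

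**Conclusion.** The concern holds as a gap in the written criteria. Four duration tests apply to Grade 4 as well as Grade 3, and the 70% rule does not catch treatment-stopping onset from day 11 under its usual reading, or from day 6 under its literal one. Days 11 to 21 are 11 of the 21 calendar days; that is a count of days, not a probability. The documents do not reproduce the grading scale, so which of the named symptoms have a Grade 4 should be checked against CTCAE v5.0.

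The effect on the 80 mg decision is probably small. Section 1.1 reports no DLT in three evaluable patients at 80 mg, so a breach of 1 in 6 needs two DLTs among the remaining three. It also reports that 120 mg was set aside on tolerability, outside the formal count. The effect cannot be bounded: the documents give no rate for short Grade 4 first-cycle events at 80 mg, and one uncounted event combined with one ordinary DLT would also matter.

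A reader might infer that patients were mis-scored or that 80 mg was wrongly chosen. Nothing in the documents shows either. Phase I may already be complete: Section 1.1 describes the expansion to six as recommended, and note e to Table 6.3 already gives 80 mg as the maximum daily dose. In that case the correction is a retrospective check. This is a cheap improvement.

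**What to change.** Amend Section 6.2 as follows:

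1. Limit the 5-, 7- and 8-day tests for the gastrointestinal symptoms, fatigue, electrolyte imbalance and immune-related events to Grade 3.
2. Add that a Grade 4 event of any of these types, of any duration, is a DLT.
3. State the delivery rule as fewer than 10 of 14 planned regorafenib doses given because of toxicity.
4. Re-check the phase I patients against the amended list and report any such event next to the DLT count as already adjudicated, not in place of it.

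Two clarifications could go into the same amendment: that treatment-related death is a DLT, and whether onset within the 21-day window is enough for a duration test completed later.

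The cost is a few words and a chart re-check, with no extra patients or procedures. The counted DLT rate may rise slightly, and the re-check applies a revised definition to patients already adjudicated, which is why both counts should be shown.

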6.3.1 Dose Modification Levels

The starting dose of regorafenib is the RD. Study medication will be administered on a 2 weeks on/1 week off schedule [2 weeks out of every 3].

Doses will be delayed or reduced for clinically significant hematologic and non-hematologic toxicities that are related to protocol therapy according to the guidelines shown in the Dose Delays/Dose Modifications table that follows. Dose modifications will follow predefined dose levels. Dose adjustments for hematologic toxicity are based on the blood counts obtained in preparation for the day of treatment.

The modifications of regorafenib will follow the following predefined dose levels:		
Dose level 2	120 mg po qd	Three 40-mg tablets of regorafenib
Dose level 1	80 mg po qd	Two 40-mg tablets of regorafenib

q.d. = *quaque die* (once daily); *q.o.d.* = *quaque altere die* (every other day)

If a subject experiences more than one toxicity, dose reduction should be according to the toxicity with the highest grade

In the case of two or more toxicities of the same grade, the investigator may dose reduce according to that deemed most causally related to study treatment. For Grade 3 toxicity it is acceptable to re-challenge with same dose level at discretion of investigator if toxicity resolved to baseline or lesser grade with medical management within 7 days.

For second occurrence of the same Grade 3 toxicity dose can be reduced to 80mg q.o.d or permanently discontinue at discretion of treating investigator and the rest of the study treatment may be continued. If a dose reduction has been performed, intra-subject dose re-escalation can be considered at the discretion of the treating physician provided that the toxicity(ies) has resolved to baseline.

Tables 6-1, 6-3, and 6-4 outline dose adjustments for toxicities related to regorafenib. Dose adjustment for liver function abnormalities is discussed in table 6-5.

Table 6-1: Recommended dose modification for toxicities except hand-foot-skin reaction, hypertension and ALT/AST/bilirubin			
NCI-CTCAE v5.0^a	Dose Interruption	Dose Modification^b	Dose for Subsequent Cycles
Grade 0-2	Treat on time	No change	No change
Grade 3	Delay until \leq Grade 2 ^c	Reduce by 1 dose level	If toxicity remains < Grade 2, dose re-escalation can be considered at the discretion of the treating investigator. If dose is re-escalated and toxicity (\geq Grade 3) recurs, institute permanent dose reduction.

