Grade 2	1 st occurrence	Consider decreasing dose by one dose level and immediately institute supportive measures. If no improvement, interrupt therapy for a minimum of 7 days, until toxicity resolves to Grade 0-1 ^{b, c}
	No improvement within 7 days or 2 nd occurrence	Interrupt therapy until toxicity resolves to Grade 0-1. ^c When resuming treatment, treat at reduced dose level ^b If dose reduced from the 1 st occurrence then discontinue therapy.
	3 rd occurrence	Discontinue therapy
	4 th occurrence	Discontinue therapy
Grade 3	1 st occurrence	Institute supportive measures immediately. Interrupt therapy for a minimum of 7 days until toxicity resolves to Grade 0-1. ^c When resuming treatment, decrease dose by one dose level. ^{b, d}
	2 nd occurrence	Discontinue therapy
	3 rd occurrence	Discontinue treatment permanently.

a. More conservative management is allowed if judged medically appropriate by the investigator.
 
b. If toxicity returns to Grade 0-1 after dose reduction, dose re-escalation is permitted at the discretion of the investigator if subject has completed one cycle at reduced dose without recurrence of event.
 
c. If there is no recovery after a 4-week delay, treatment with regorafenib will be discontinued permanently.
 
d. Subjects requiring > 1 dose reductions should go off protocol therapy.
 
e. The maximum daily dose is 80 mg. If reduction required resulting in a dose of less than 80mg qod of regorafenib, then regorafenib will be permanently discontinued.
		

Specific guidance for skin and subcutaneous disorders other than HFSR (includes rash, rash erythematous, rash follicular, rash generalized, rash macular, rash maculopapular, rash papular, rash pruritic, exfoliative rash, pruritus, eczema, dermatitis)		
Event	Regorafenib	Pembrolizumab
G2	
 No modifications 	
 Consider withholding for persistent symptoms Restart at same dose if resolution to ≤ G1 or baseline ≤ 12 weeks of last infusion Consider discontinuation if NO resolution ≤ 12 weeks of last infusion ¹

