G3	
 • Hold until recovery to \leq G2 and restart at same dose level or reduce 1 dose level ^a (at the investigator's discretion) • 1st + 2nd re-appearance: Hold until recovery to \leq G2 and reduce 1 dose level ^a (at the investigator's discretion) • 3rd re-appearance: Discontinue 	
 • Hold and restart at same dose if resolution to \leq G1 or baseline \leq 12 weeks of last infusion • Hold and discontinue if NO resolution \leq 12 weeks of last infusion ^b
G4 (when applicable)	
 • Hold until recovery to \leq G2 and reduce 1 dose level ^a • 1st re-appearance: Discontinue 	
 • Discontinue ^b

¹ If toxicity returns to Grade 0-1 after dose reduction, dose re-escalation is permitted at the discretion of the investigator if subject has completed one cycle at reduced dose without recurrence of event.

a: If reductions are required resulting in a dose of less than 80 mg q.o.d. of regorafenib, then regorafenib will be permanently discontinued. For grade 3, patient could stay on regorafenib for the first appearance, or hold until resolved to grade 2 or less, restart at the same dose level or lower after discussion between investigator and study chair.

b: after consultation with study chair, if toxicity considered at least possibly related to pembrolizumab.

If reduction required resulting in a dose of less than 80mg qod of regorafenib, then regorafenib will be permanently discontinued.

(For studies with combination therapy, consider including the following statement "The other study treatment may be continued").

At first occurrence of HFSR, independent of grade, prompt institution of supportive measures such as topical emollients, low potency steroids, or urea-containing creams should be administered.

Recommended prevention/management strategies for skin toxicities consistent with HFSR are summarized below:

Control of calluses

Before initiating treatment with regorafenib:

- Check condition of hands and feet.
- Suggest a manicure/pedicure, when indicated.
- Recommend pumice stone use for callus or 'rough spot' removal.

During regorafenib treatment:

- Avoid pressure points.
- Avoid items that rub, pinch or create friction.

Use of creams

- Non-urea based creams may be applied liberally.

- Keratolytic creams (e.g. urea-based creams, salicylic acid 6%) may be used sparingly and only to affected (hyperkeratotic) areas.

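### Read literally, the 70% dose-delivery DLT rule needs 10 of 14 cycle 1 regorafenib doses lost, whereas its stated purpose fits a trigger at 5

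*Combined protocol and SAP*

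**What the plan says.** Section 6.2 lists haematological, liver and other DLTs. Under combination therapy it adds a criterion for toxicity that meets none of them: "When 70% of the planned regorafenib dose cannot be administered because of toxicity other than DLT during the DLT evaluation period". The reason follows at once: "This criteria is in place to ensure the combination can be delivered safely".

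The separate skin criterion in Section 6.2 covers "Grade 3 dermatologic toxicity (HFSR and non-life threatening events") only if it lasts 7 or more consecutive days. Grade 4 counts at any duration. There is no skin criterion for Grade 2.

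Section 6.3.1, Table 6.3, suggests holding regorafenib for HFSR. For a first Grade 2 event that does not improve, the advice is to "interrupt therapy for a minimum of 7 days, until toxicity resolves to Grade 0-1". A first Grade 3 event carries the same 7-day minimum and the same recovery target.

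Section 6.1 plans regorafenib on days 1 to 14 of a 21-day cycle. Section 6.2 bases escalation on DLTs in the first cycle and does not accept a dose level with more than 1 DLT in 6 patients.

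**The concern.** As written, the sentence makes the lost share, not the delivered share, reach 70%. A patient could miss 9 of 14 doses because of toxicity and still be scored as free of DLT. That sits badly with a rule meant to show that the combination can be delivered. Nothing else in the document says which share is meant.

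The threshold matters because first-course DLT is the phase I endpoint (Section 10), and because this rule is the only one that catches toxicity which stops dosing without meeting a listed criterion. The protocol's own 7-day HFSR hold produces losses in the disputed range. 80 mg is the lowest level listed in Section 6.1, so its score out of six decides whether a listed dose goes forward.

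**Working it through.** The plan gives no dose count for this rule, so there is no figure to reproduce.

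**Inputs**
- Planned cycle 1 doses: 14 (Section 6.1).
- Threshold: 70% (Section 6.2).
- HFSR hold: at least 7 days (Table 6.3).
- Status at 80 mg: three evaluable patients with no DLT, three more to enrol (Section 1.1).
- Assumptions: full dosing before the hold, and no missed doses made up in the week off.

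**Step 1. Thresholds, with k doses lost**
- Literal reading: smallest k with k/14 ≥ 0.70. Since 0.70 × 14 = 9.8, k = 10 (10/14 = 71.4% lost). At k = 9 the loss is 64.3%, not a DLT.
- Purpose reading: smallest k with (14 − k)/14 < 0.70. This needs k > 4.2, so k = 5 (9/14 = 64.3% given). At k = 4, 71.4% is given, not a DLT.
- The readings disagree at 5 to 9 doses lost.

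**Step 2. A 7-day hold starting on day s, restarted at the same dose**

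Doses lost = min(7, 15 − s).

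| Start day | Lost | Given | Literal reading | Less than 70% given |
|---|---|---|---|---|
| By day 8 | 7 | 50.0% | not a DLT | DLT |
| 9 | 6 | 57.1% | not a DLT | DLT |
| 10 | 5 | 64.3% | not a DLT | DLT |
| 11 | 4 | 71.4% | not a DLT | not a DLT |
| 12 or later | 3 or fewer | 78.6% or more | not a DLT | not a DLT |

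**Step 3. Holds longer than the minimum**

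A hold from day s can lose at most 15 − s doses, and 15 − s ≥ 10 requires s ≤ 5. A hold of 7 days or more that starts on days 6 to 10 therefore loses 5 to 9 doses, however long it lasts and whatever dose follows. A start by day 5 meets both readings if the hold reaches 10 days. With a shorter hold and a same-dose restart, it stays in the gap. A reduced restart after such an early hold would add to the loss; I put no figure on it, because the step below 80 mg after a first event is not clearly set.

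**Step 4. Which patients only this rule can catch**
- Grade 3 HFSR lasting under 7 days: the skin criterion is not met, but the hold continues until Grade 0-1.
- Grade 2 HFSR without improvement: no skin criterion applies. If lack of improvement is judged after 7 days, as in the second Grade 2 row of Table 6.3, onset must be by day 3 for the hold to start by day 10 (3 + 7 = 10).
- Other Grade 3 rash: the hold has no fixed length. With a same-dose restart, it falls in the gap only if it runs 5 or 6 days and starts by day 10. Grade 3 rash lasting 7 days is already a DLT.

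**Step 5. Effect on the dose decision**

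The count stands at 0 of 3. Exceeding 1 of 6 needs 2 DLTs among the remaining 3. One disputed case alone moves 0/6 to 1/6 and changes nothing. One disputed case plus one other DLT moves 1/6 to 2/6. Two disputed cases move 0/6 to 2/6.

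**The case against.** The strongest reply is that this is loose drafting with little left to affect. The purpose sentence already points to the sensible reading. DLT calls are settled by deliberation between subsites and the principal investigator, with weekly safety meetings, and a Phase I DLT Committee reviewed the first patients. Half of the six 80 mg patients are already scored. Section 6.3.1 also opens with "The starting dose of regorafenib is the RD", and footnote e of Table 6.3 gives 80 mg as the maximum daily dose, which suggests that phase II at 80 mg was already in view.

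The small exposure stands. The rest stands only in part. Adjudicators apply a criterion, and nothing tells them which of two thresholds it sets. No other dose-modification rules are given for phase I, and Section 1.1 still describes 80 mg patients to be reviewed.

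It is also fair that holds are partly discretionary. Table 6.3 makes suggestions, and for other rash the skin table says "For grade 3, patient could stay on regorafenib for the first appearance, or hold until resolved to grade 2 or less". A patient dosed throughout at full dose loses nothing under either reading.

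A reader might go further in four ways that the documents do not support:
- That the ambiguity shaped the decision on 120 mg. Section 1.1 places those rash reductions in cycle 2 or 3, outside the DLT window.
- That an early 80 mg hold would be a DLT on either reading because dosing resumes every other day. Section 6.3.1 attaches that step ("dose can be reduced to 80mg q.o.d or permanently discontinue at discretion of treating investigator") to a second occurrence of the same Grade 3 toxicity.
- That Section 5.2.3 already bars replacing a held patient. It concerns dropouts, whom Section 5.2.2 defines as leaving the study. Whether a held patient is evaluable, given that Section 6.2 describes the first cycle as uninterrupted, is a separate open question.
- That the rule must be computed in mg, or must count every discretionary hold. The text settles neither.

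**Conclusion.** The point holds as a wording fault in a decision threshold. The literal trigger is 10 of 14 doses lost, the trigger that fits the stated purpose is 5, and HFSR holds under Table 6.3 starting by day 10 can fall between them. These counts are exact under the assumptions listed.

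The consequence is limited. It reaches the dose decision only if at least two of the three remaining 80 mg patients have a DLT or a disputed hold, at least one of them a disputed hold. The documents give no cycle 1 rate for these events at 80 mg, so no frequency is claimed. A reader might infer that the three patients already reviewed were misclassified or should be re-scored. Section 1.1 reports them as evaluable with no DLT and says nothing of doses lost in cycle 1, so that inference has no basis.

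**What to change.** Replace the 70% sentence in Section 6.2, prospectively, with: *If less than 70% of the planned cycle 1 regorafenib dose can be administered because of toxicity that does not otherwise meet a DLT criterion, this is a DLT.* Score the remaining 80 mg patients by it, and leave the completed reviews as they are.

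The cost is one sentence in an amendment and a reading of cycle 1 pill diaries, which the study calendar already collects. Treatment, sample size and the 7-day skin criterion do not change. The downside is that some held Grade 2 HFSR cases, and some Grade 3 cases shorter than 7 days, will count as DLTs. If the sponsor does not want that, the exception should be written into the same sentence.
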